11.4.4 Analyses of other endpoints

The antibody status (positive/negative) and antibody titers will be summarized by visit using descriptive statistics. If appropriate, correlations between antibody titers, safety and/or efficacy endpoints will be provided by graphical methods.

The number (n) and percentage (%) of patients with an up-titration to 150 mg of alirocumab will be described as well as the detailed reasons that trigger the up-titration for patients for whom the parent study was not ODYSSEY High FH.

10-Jul-2015 Version number: 1

The number (n) and percentage (%) of patients with a down-titration to 75 mg of alirocumab will be described as well as the detailed reasons that trigger the down-titration.

Further details will be provided in SAP.

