8.4 METHOD OF ASSIGNING PATIENTS TO TREATMENT GROUP

This is an open-label study and every patient will receive alirocumab. Treatment kit numbers will be allocated via interactive voice/web response system (IVRS/IWRS). Patients will keep the same identification number that they were allocated in the parent study.

From Week 12 (Visit 4), the Investigator will manage, based on his/her own judgment and LDL-C value from sample obtained at the previous scheduled visit, adjustment of alirocumab doses (either up-titration from 75 mg to 150 mg every 2 weeks or down-titration from 150 mg to 75 mg every 2 weeks, or maintenance of the dose, will be possible). For adjustments based on LDL-C values, simultaneous adjustments in alirocumab dose and any LMT should be avoided.

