10.6.2.1 Allergic events with cutaneous involvement

Adverse events with cutaneous involvement which are obviously of allergic origin or injection site reactions which progress/expand/worsen/etc should be evaluated by a dermatologist as soon as possible, and preferably within one week of the site first becoming aware of the event.

The investigator should evaluate the patient for possible etiologies (new medications, etc) and extra-cutaneous symptoms and signs. An unscheduled Central Laboratory assessment for hematology, chemistry, liver panel and ADA should be obtained. If it is possible, the site will take pictures of the skin lesions in order to provide the patient with them for the dermatologist's visit.

If the photos are obtained, then copies should be kept as source documents which may later be collected by the sponsor. The investigator will provide a summary of the patient's case, reason for consultation, and information being requested to the consulting dermatologist.

A full consultation report should be sent by the dermatologist to the investigator. The full report should contain, at a minimum, the following information; a detailed description of the rash (such as the morphology [lesion type], shape of individual lesions, arrangement of multiple lesions [eg, scattered, grouped, linear, etc.], distribution, color, consistency, presence of pruritus or pain, and other clinical signs) and in case a skin biopsy (including histopathology and immunofluorescence) was done (if it was deemed necessary as per the dermatologist's or investigator's medical judgment), the results of this investigation with, if applicable, a specific diagnosis of the AE. The investigator will fax the full report and the corrected AE form if necessary, to the Monitoring Team Representative within 24 hours.

10-Jul-2015 Version number: 1

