#### 2.1.6 Anti-alirocumab antibodies variables

Anti-alirocumab antibodies (ADA) are assessed at Week 0 (before the IMP injection in OLE study), Week 24, Week 48, Week 72, Week 96, Week 120, Week 144 and Week 168)/or early termination .

ADA measurements will be assigned to similar analysis windows as defined for efficacy parameters (Table 1).

• The following variables will be described: ADA response (Positive or Negative).

For ADA positive:

- Titer levels
- Neutralizing status (Positive or Negative)
- Pre-existing positive ADA defined as patients with positive ADA response at baseline of the parent study with less than 4-fold increase in titer during the OLE period
- Treatment-emergent ADA positive response during the OLE period, defined as:
  - Patients with no positive ADA response at baseline of the parent study but with a positive response ADA response during the OLE period; OR
  - Patients with positive ADA response at baseline of the parent study and at least 4-fold increase in ADA titer during the OLE period.

Treatment-emergent ADA positive responses during the OLE period will be described according to the ADA status during the double-blind period (Pre-existing, Negative and Treatment-emergent ADA status).

For treatment emergent positive ADA during the OLE period, the following categories for ADA duration will be applied:

- A persistent positive response is a treatment-emergent ADA positive response detected in at least 2 consecutive samples post first OLE injection separated by at least a 12-week period
- An indeterminate duration positive response is defined as ADA present only at the last sampling time point in OLE period
- A transient positive response is defined as any treatment-emergent positive ADA response that is neither considered persistent nor indeterminate

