#### 2.3.2.1 Anti-alirocumab antibody population

The anti-alirocumab antibody analysis will be performed on all treated patients (safety population) with an available ADA sample at baseline from parent study and at least one available ADA sample post first open-label IMP injection.

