# 2.4.7 Analyses of anti-alirocumab antibodies variables

The following summaries will be performed on the ADA population, overall as well as according to treatment received in the parent study (placebo versus alirocumab (regardless of dose)), taking into account all samples collected during the current study regardless of timing in relation to injections:

- ADA results (negative or positive) by time point;
- Neutralizing status (negative or positive) by time point for positive ADA;
- ADA titers using descriptive statistics (median, minimum and maximum) for positive ADA by time point;
- Number (%) of patients with treatment-emergent ADA positive response during the OLE period, overall and according to ADA status during the double-blind period (Pre-existing ADA, Negative ADA status and Treatment emergent ADA status)
- Number (%) of patients with persistent/transient/indeterminate treatment-emergent ADA positive response, overall and according to ADA status during the double-blind period (Pre-existing ADA, Negative ADA status and Treatment emergent ADA status)
- Time to onset of treatment-emergent ADA positive response during the OLE period using descriptive statistics.

Correlations between ADA parameters (eg, titers, treatment-emergent ADA positive status, neutralizing status) and safety and/or efficacy endpoints will be also explored (eg, scatter plot).

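### The antibody–efficacy correlation accounts for neither dose nor titration, although every scheduled antibody sample after the first OLE injection follows the opening of LDL-C-based dose adjustment, so any antibody-related loss of effect is likely to look smaller than it is

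*Protocol*

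**What the plan says.** - **Correlation.** Protocol 11.4.4 names titers only and makes the display conditional: "If appropriate, correlations between antibody titers, safety and/or efficacy endpoints will be provided by graphical methods". SAP 2.4.7 widens it: "Correlations between ADA parameters (eg, titers, treatment-emergent ADA positive status, neutralizing status) and safety and/or efficacy endpoints will be also explored (eg, scatter plot". Neither states a visit pairing, a dose term or a titration term.
- **Antibody sampling.** SAP 2.1.6: "Anti-alirocumab antibodies (ADA) are assessed at Week 0 (before the IMP injection in OLE study), Week 24, Week 48", then every 24 weeks to Week 168 or early termination. Protocol 10.6.2.1 can add samples after an allergic event involving the skin: "An unscheduled Central Laboratory assessment for hematology, chemistry, liver panel and ADA should be obtained".
- **Samples used.** SAP 2.4.7 summarises ADA "taking into account all samples collected during the current study regardless of timing in relation to injections". The only split by treatment is by parent-study arm, ignoring dose. Treatment-emergent ADA is also described by double-blind ADA status.
- **Titration.** From Week 12, under Protocol 8.4, "the Investigator will manage, based on his/her own judgment and LDL-C value from sample obtained at the previous scheduled visit, adjustment of alirocumab doses". Protocol 8.8.1 also lets background LMT be adjusted on the investigator's judgment.
- **Titration tables.** SAP 2.4.3.1 summarises titrations, their reasons and the associated LDL-C, overall and by visit. Its example subgroup factors are cardiovascular history and region; ADA status is not named.

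**The concern.** Up-titration is partly a consequence of the effect under study. If antibodies weaken the LDL-C response, the Week 8 value is higher and the patient is more likely to receive a higher dose or more background therapy. The Week 24 LDL-C is then lower than it would have been. A plot of ADA against LDL-C at that visit compares patients after investigators have already closed part of the gap. Down-titration of patients with very low LDL-C pushes the same way.

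The bias runs in the reassuring direction. Part of the loss would appear instead as extra up-titrations among ADA-positive patients, and no planned table shows those by ADA status. A statement that antibodies do not affect efficacy could then rest on a display that leans toward that answer.

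**Working it through.** The plan states no effect size, ADA prevalence or up-titration rate, so there is no figure to reproduce. The check is a comparison of schedules followed by an illustration on assumed values.

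**Step 1: schedules** (Protocol 1.2 and 8.4; SAP 2.1.6 and Table 1)

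| Item | OLE weeks |
|---|---|
| Scheduled ADA | 0 (pre-dose), 24, 48, 72, 96, 120, 144, 168 |
| Scheduled LDL-C | 0, 8, 24, 48, 72, 96, 120, 144, 168 |
| Dose adjustment possible | from 12 |

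Between the first OLE injection and Week 12 there are no scheduled ADA samples and one scheduled LDL-C sample (Week 8). The SAP's Week 24 window opens on Day 155; the Week 12 visit is Day 85. That leaves 155 − 85 = 70 days, or five two-week injection intervals, in which a dose change can act.

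**Step 2: who can be up-titrated.** Protocol Section 4 gives heFH patients randomized in the parent studies: 486 + 249 + 107 + 385 = 1,227. If all enrolled, the 107 from High FH start on 150 mg and 1,227 − 107 = 1,120 (91%) start on 75 mg.

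**Step 3: simple formula.** Let L be the true ADA-related loss in percentage points of LDL-C change, g the extra lowering from up-titration, and p1 − p0 the excess share up-titrated among affected patients.

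Observed difference = L − (p1 − p0) × g; attenuation = (p1 − p0) × g / L.

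With L = 20 assumed:

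| p1 − p0 | g | Observed | Attenuation |
|---|---|---|---|
| 0.3 | 10 | 17.0 | 15% |
| 0.3 | 15 | 15.5 | 23% |
| 0.6 | 10 | 14.0 | 30% |
| 0.6 | 15 | 11.0 | 45% |

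**Step 4: simulation in which titration follows LDL-C.** Assumptions, with 1,000,000 virtual patients per scenario: parent-baseline LDL-C mean 150 mg/dL, SD 45; percent change on the starting dose mean −45, SD 15; visit noise SD 8; L = 10, 20 or 30; up-titration with probability 0.5 or 1.0 when Week 8 LDL-C is at or above 70 or 100 mg/dL; g = 10 or 20. None of these is an OLE rule or result in the documents.

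- At Week 8 the ADA-positive minus ADA-negative difference equals the full assumed loss.
- At Week 24, pooled over dose, 70% to 95% of it remains, an attenuation of 5% to 30%. For L = 20 the difference is 14.1 to 18.7 points.
- Split by current dose, L = 20 gives 17.1 to 21.1 points in patients not up-titrated and 14.1 to 16.2 in those up-titrated. Splitting does not reliably restore the 20, because dose was chosen on LDL-C.

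The two ranges differ because of the excess share. For L = 20 the simulation produces 0.12 (0.42 − 0.30) to 0.30 (0.59 − 0.29), against 0.3 to 0.6 assumed in Step 3. At 0.30 with g = 20 the formula gives 0.30 × 20 / 20 = 30%, matching the simulated maximum.

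**The case against.** A reader might infer that the correlation uses only samples taken after titration opened. The documents do not say so. A Week 0 sample is scheduled, unscheduled and early-termination samples can precede Week 12, and the SAP counts all OLE samples. Pairing is left open, so per-patient ADA status could be set against Week 8 LDL-C. This stands, and it limits the point to scheduled samples after the first injection. It does not repair the plan, because nothing commits to that pairing. Week 0 precedes any alirocumab exposure in parent-placebo patients, and by the SAP's own account (2.4.4.2) follows a 10-week washout in LTS11717 patients.

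A reader might also infer that titration hides an antibody effect. That is not supported: on every set of assumptions above, more than half of it remains visible. Titration is discretionary, and antibodies that first arise after a dose change cannot have caused it. Neither calculation models down-titration, patients already on 150 mg or LMT changes.

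Finally, this is one exploratory display in an uncontrolled, descriptive study, and most of the immunogenicity objective is served by the incidence, titer, persistence and time-to-onset summaries. The titration subgroup factors are only examples, so ADA is unlisted rather than excluded. All of that is fair and keeps the point modest. Yet SAP 2.4.4.2 deliberately uses OLE Week 8, before titration, for its own dose-effect comparisons; the ADA correlation has no equivalent protection.

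**Conclusion.** The point holds in a limited form. No scheduled ADA sample falls between the first OLE injection and the opening of LDL-C-based dose adjustment, and the planned correlation ignores dose and titration. To the extent that titration and LMT changes respond to LDL-C, a dose-pooled ADA-versus-LDL-C plot at Week 24 or later is biased toward no effect. The expected result is attenuation, not concealment. Its size is unknown; about 5% to 45% spans both illustrations, and the upper end needs an excess of 60 percentage points in up-titration among affected patients. The direction is firmer than the size. It rests on poorer LDL-C making up-titration or LMT intensification more likely, which fits the protocol's basis for titration but is not fixed by any threshold.

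**What to change.** Amend SAP 2.4.7; analysis only, with no change to dosing or sampling.

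1. Among patients starting the OLE on 75 mg, tabulate up-titration for LDL-C, and LMT intensification, by treatment-emergent ADA status and by neutralizing status. Note whether ADA was first detected before or after the change.
2. In parent-alirocumab patients, relate Week 0 and parent-study ADA status to the Week 8 percent change in LDL-C, by parent study, since LTS11717 patients enter after a washout. For ADA at later visits, present LDL-C only up to the first dose or LMT change. State that patients changed at Week 12 contribute LDL-C that predates their first scheduled post-injection ADA sample, and that those still unchanged at later visits are a selected group.
3. Mark the dose in use on the plots for display only. Base no statement about ADA and efficacy on the dose-pooled or dose-split plots alone.

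The cost is SAP wording, a table and re-coded plots; dose, titration reason, LMT and ADA data are already collected. The drawbacks are few ADA-positive patients per cell, and that ADA first arising in the OLE is seen on schedule only from Week 24, which no re-analysis can change.

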11.4.4.1 Analyses of quality of life/health economics variables

The analysis of data from EQ-5D instrument will be performed on efficacy population.

Descriptive summaries for individual EQ-5D items.

• Frequency and proportion of patients within each EQ-5D domain and response categories will be summarized by visits on which EQ-5D is assessed (Weeks 0,12, 24, 48, and End of OLETP)

Descriptive summaries for EQ-5D utility scores.

• Response from individual items will be converted into a single EQ-5D utility score by means of a standard regression model. Summary statistics for the utility score (number, mean, median, Q1, Q3, standard deviation, minimum and maximum) will be calculated by visits on which EQ-5D is assessed (Weeks 0, 12, 24, 48, and End of OLETP). Change in mean EQ-5D utility scores from baseline (Week 0) to Weeks 12, 24, 48, and End of OLETP, will be calculated.

Further details will be provided in SAP.

11.5 INTERIM ANALYSIS

Interim analyses might be performed if requested by Health Authorities or if needed for the purpose of scientific communication.

12 ETHICAL AND REGULATORY STANDARDS

12.1 ETHICAL PRINCIPLES

This clinical trial will be conducted in accordance with the principles laid down by the 18th World Medical Assembly (Helsinki, 1964) and all applicable amendments laid down by the World Medical Assemblies, and the ICH guidelines for good clinical practice (GCP).

In compliance with Sanofi public disclosure commitments, this clinical trial will be recorded in the public registry website clinicaltrials.gov before the enrollment of the first patient. The registry will contain basic information about the trial sufficient to inform interested patients (and their healthcare practitioners) how to enroll in the trial.

12.2 LAWS AND REGULATIONS

This clinical trial will be conducted in compliance with all international guidelines, and national laws and regulations of the country(ies) in which the clinical trial is performed, as well as any applicable guidelines (see Section 13.1).

12.3 INFORMED CONSENT

The Investigator (according to applicable regulatory requirements), or a person designated by the Investigator, and under the Investigator's responsibility, should fully inform the patient of all pertinent aspects of the clinical trial including the written information giving approval/favorable opinion by the Ethics Committee (IRB/IEC). All participants should be informed to the fullest extent possible about the study, in language and terms they are able to understand.

Prior to a patient's participation in the clinical trial, the written informed consent form should be signed, name filled in and personally dated by the patient or by the patient's legally acceptable representative, and by the person who conducted the informed consent discussion. A copy of the signed and dated written informed consent form will be provided to the patient.

The informed consent form used by the Investigator for obtaining the patient's informed consent must be reviewed and approved by the Sponsor prior to submission to the appropriate Ethics Committee (IRB/IEC) for approval/favorable opinion.

12.4 INSTITUTIONAL REVIEW BOARD/INDEPENDENT ETHICS COMMITTEE (IRB/IEC)

As required by local regulation, the Investigator or the Sponsor must submit this clinical trial protocol to the appropriate Ethics Committee (IRB/IEC), and is required to forward to the respective other party a copy of the written and dated approval/favorable opinion signed by the Chairman with Ethics Committee (IRB/IEC) composition.

10-Jul-2015 Version number: 1

The clinical trial (study number, clinical trial protocol title and version number), the documents reviewed (clinical trial protocol, informed consent form, Investigator's Brochure, Investigator's curriculum vitae [CV], etc) and the date of the review should be clearly stated on the written (IRB/IEC) approval/favorable opinion.

IMP will not be released at the study site and the Investigator will not start the study before the written and dated approval/favorable opinion is received by the Investigator and the Sponsor.

During the clinical trial, any amendment or modification to the clinical trial protocol should be submitted to the Ethics Committee (IRB/IEC) before implementation, unless the change is necessary to eliminate an immediate hazard to the patients, in which case the IRB/IEC should be informed as soon as possible. It should also be informed of any event likely to affect the safety of patients or the continued conduct of the clinical trial, in particular any change in safety. All updates to the Investigator's Brochure will be sent to the Ethics Committee (IRB/IEC).

A progress report is sent to the Ethics Committee (IRB/IEC) at least annually and a summary of the clinical trial's outcome at the end of the clinical trial.

13 STUDY MONITORING

13.1 RESPONSIBILITIES OF THE INVESTIGATOR(S)

The Investigator(s) and delegated Investigator staff undertake(s) to perform the clinical trial in accordance with this clinical trial protocol, ICH guidelines for Good Clinical Practice and the applicable regulatory requirements.

The Investigator is required to ensure compliance with all procedures required by the clinical trial protocol and with all study procedures provided by the Sponsor (including security rules). The Investigator agrees to provide reliable data and all information requested by the clinical trial protocol (with the help of the CRF, Discrepancy Resolution Form [DRF] or other appropriate instrument) in an accurate and legible manner according to the instructions provided and to ensure direct access to source documents by Sponsor representatives.

If any circuit includes transfer of data particular attention should be paid to the confidentiality of the patient's data to be transferred.

The Investigator may appoint such other individuals as he/she may deem appropriate as Subinvestigators to assist in the conduct of the clinical trial in accordance with the clinical trial protocol. All Subinvestigators shall be appointed and listed in a timely manner. The Subinvestigators will be supervised by and work under the responsibility of the Investigator. The Investigator will provide them with a copy of the clinical trial protocol and all necessary information.

13.2 RESPONSIBILITIES OF THE SPONSOR

The Sponsor of this clinical trial is responsible to health authorities for taking all reasonable steps to ensure the proper conduct of the clinical trial protocol as regards ethics, clinical trial protocol compliance, and integrity and validity of the data recorded on the CRFs. Thus, the main duty of the monitoring team is to help the Investigator and the Sponsor maintain a high level of ethical, scientific, technical and regulatory quality in all aspects of the clinical trial.

At regular intervals during the clinical trial, the site will be contacted, through monitoring visits, letters or telephone calls, by a representative of the monitoring team to review study progress, Investigator and patient compliance with clinical trial protocol requirements and any emergent problems. These monitoring visits will include but not be limited to review of the following aspects: patient informed consent, patient recruitment and follow-up, SAE documentation and reporting, AESI documentation and reporting, AE documentation, IMP allocation, patient compliance with the IMP regimen, IMP accountability, concomitant therapy use and quality of data.

13.3 SOURCE DOCUMENT REQUIREMENTS

According to the ICH guidelines for Good Clinical Practice, the monitoring team must check the CRF entries against the source documents, except for the pre-identified source data directly recorded in the CRF. The informed consent form will include a statement by which the patient allows the Sponsor's duly authorized personnel, the Ethics Committee (IRB/IEC), and the regulatory authorities to have direct access to original medical records which support the data on the CRFs (eg, patient's medical file, appointment books, original laboratory records, etc). These personnel, bound by professional secrecy, must maintain the confidentiality of all personal identity or personal medical information (according to confidentiality and personal data protection rules).

